Research hypothesis: Patients who are seen during a virtual phone visit will report different PRO and patient satisfaction scores compared to patients who are seen during an in-person visit for post-operative follow-up at 6 weeks, 12 weeks, and 6-months.

5) Background

Since the WHO declared the coronavirus disease 2019 (COVID-19) a global pandemic on March 11, 2020, health systems have had to reorganize and change the way healthcare is provided to patients [1]. An emphasis has been placed on social distancing to limit the spread of the severe acute respiratory syndrome coronavirus 2 (SARS-CoV-2). In the past several months, healthcare has rapidly shifted towards telemedicine to limit the COVID-19 spread. Telemedicine is defined as healthcare where clinicians utilize technology and telecommunications to treat and diagnose patients [2]. Benefits of telemedicine has been found to include decrease healthcare costs, decrease overall appointment times, and similar patient satisfaction [3-4]. During the age of COVID-19, telemedicine has played a vital role in allowing the conservation of resources like personal protective equipment (PPE), decrease in risk of clinician exposure to COVID-19, and maintain social distancing.

Telemedicine has been researched in various medical specialties and have been associated with good outcomes and patient satisfaction scores [5]. Based on the literature, the use of telemedicine in orthopedics has not been extensively studied. There are studies on virtual fracture clinics which have grown in use in the United Kingdom and Ireland, however, they do not utilize a live assessment model [6-8]. One study looks at patient satisfaction of those seen at a regional medical center in rural Norway through telemedicine [9]. Also, there are studies exploring the use of telemedicine to provide follow-up care after

Patient reported outcomes from patients seen in virtual phone visits compared to in-person physical visits for post-operative follow-up at a sports medicine clinic: a prospective randomized controlled trial

total hip and knee arthroplasty [10-13] and the role of telemedicine by physical therapists as a viable option for virtual rehabilitation [14]

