Researchers want to allow patients to have enough time to read the information sheet and consider participation in this study.

In-person consent will be done at any in-person visit including the pre-operative appointment, day of surgery, and at the routine 2-week postop visit.

How: The Participant will be recruited in-person.

Source of the Participants: Patients that present to the Harbor-UCLA Medical Center sports medicine clinic that have scheduled operative intervention.

Methods to identify potential Participants: When patients of the sports medicine clinic have planned operative intervention, study team member will go through the patient charts to see if patient meets criteria and then discuss and consent the Participant in-person.

Materials to recruit Participants: Patients who meet criteria will be given the information study sheet to review on their own.

Patient reported outcomes from patients seen in virtual phone visits compared to in-person physical visits for post-operative follow-up at a sports medicine clinic: a prospective randomized controlled trial

There are no payments to any of the Participants.

b) Inclusion and Exclusion Criteria

Inclusion criteria:

Participants are at least 18 years of age. Participants who are seen at Harbor-UCLA Medical Center sports medicine clinic. Participants have agreed to have operative intervention. Participants must own a phone with reliable calling capabilities. The Participants must have access to reliable internet to fill out the online survey. The Participants must be able to provide consent. Participants may include pregnant patients. Participants who start out in the virtual phone pathway, and the clinician deems person to require an in-person appointment at the 2-week follow-up visit can be moved to the in-person pathway.

Exclusion criteria:

Patients that are under the age of 18, any cognitive impaired adult, and any adult unable to provide consent.

c) Local Number of Participants

For a statistical significance of 0.05, Power of 80%, and assuming a medium effect size of 0.8, 26 patients are required per group for a total of 52 Participants.

The number of Participants need to complete the research procedure are 52.

Locally we will attempt to recruit at least 104 Participants. This will allow room in case of patients are removed or fall from the study.

d) Study-Wide Number of Participants

This is not a multicenter study.

e) Study Timelines

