The first page of the survey asks for the Participant's name, date of birth, and preferred language (English or Spanish), how comfortable filling out the form, who is completing the form, which joints, amount of pain, and amount of back pain. The second page of the survey will be a joint specific survey and will depend on the joint selected on the first page and the language chosen. It can be the KOOS, QuickDash Outcome Measure, or PROMIS Global. There is a separate patient satisfaction survey that the patient will complete.

Participants will have appointments with the surgeon for suture removal (10 to 14 days after surgery), and evaluation at 6 weeks, 12 weeks, and 6 months after surgery per usual practice.

The source records that will be used to collect data about the Participants are the surveys, and type of surgery, and results of follow up visits. The data collected will be asked on the surveys which include demographic information- Participants' injury region, age, gender, and time since operative intervention.

Study coordinator will check the upcoming Participant schedule and ensure the correct appointment is scheduled.

h) Data and Specimen Banking

None. No data or specimen banking will be done.

i) Data Management/Statistical Analysis

Statistical analysis will be conducted to compare the total scores of each survey results from participants in the in-person group with participants in the virtual phone group. Each Participant outcomes scores will be averaged with standard deviation calculated.

Participant outcomes scores from each appointment time frame (6-week, 12 week, and 6 months) will be compared across the in-patient group and virtual phone group using Student t-test. Statistical significance will be based on an α level of 0.05.

To determine if there is a difference among the Participants' preference for an in-person visit or telemedicine visit, we will conduct a chi-squared test comparing the percentage of Participant responses from the in-patient group with responses from virtual phone group.

Within each category, to determine if Participant's satisfaction changed as time progressed, we will conduct an Analysis of Variance. This will help us determine

Patient reported outcomes from patients seen in virtual phone visits compared to in-person physical visits for post-operative follow-up at a sports medicine clinic: a prospective randomized controlled trial

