if Participants who experience virtual phone visits start to have changing satisfaction the longer time has elapsed since initial operative intervention.

The PROMIS Global is used to calculate the required sample size as it is the largest range of the outcome measures resulting in the most conservative estimates.

For a statistical significance of 0.05, Power of 80%, and assuming a large effect size of 0.8, 26 Participants are required per group for a total of 52 Participants.

At the end, study data will be exported into excel sheets. All the data collected will be on an excel spreadsheet for purposes of the study. Individual surveys will not be downloaded. At that time, all identifiers will be removed and a de-identified data set is maintained and analyzed. At this time, the study team will not be able to identify which data belongs to which participant. Once this occurs, a subject will not be able to request removal of their data. This spreadsheet will be stored on the secure One Drive Microsoft account which uses double authentication and is provided to all DHS employees. Data originating from the surveys will also be kept in a password-protected location on the Harbor-UCLA One Drive Microsoft account. Data will be stored for 3 years after study completion. Access to the data will be given only to those registered with the study.

Signed consent documents any other paper records are kept in a locked cabinet in a locked office with limited access. The data will be stored for 3 years after completion of the research project.

The only individuals with access to the information will be members of the study team.

j) Confidentiality

A list of Participants participating in the study will include the Participant's name, element of dates, which experiment group the Participant is a part of, MRN, and phone number and email, and study ID number. No health information is recorded with this list. This list is kept on the Harbor-UCLA One Drive Microsoft account and available to the research team. All health data required will be recorded in REDCap hosted by Lundquist and the data will include direct identifiers such as name.

k) Provisions to Monitor the Data to Ensure the Safety of Participants

This research does not result in more than minimal risk to the Participants.

l) Withdrawal of Participants

Participants can withdraw from the study at any time.

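### Separate t-tests at each visit leave earlier scores unused when participants are later lost; this costs precision, and can bias the arm comparison if loss differs by arm or the arms already differ

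*Combined protocol and SAP*

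**What the plan says.** The hypothesis in section 4 is that phone-visit patients "will report different PRO and patient satisfaction scores compared to patients who are seen during an in-person visit" at the three follow-up times. The only between-arm analysis of outcome scores is in section 9i: scores from each time frame "will be compared across the in-patient group and virtual phone group using Student t-test" (the in-patient group is evidently the in-person arm). It adds that "Statistical significance will be based on an α level of 0.05". The only analysis over time is an analysis of variance of satisfaction within each group, which does not compare the arms.

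On numbers, section 9i states: "For a statistical significance of 0.05, Power of 80%, and assuming a large effect size of 0.8, 26 Participants are required per group". Section 9c adds "The number of Participants need to complete the research procedure are 52" and "Locally we will attempt to recruit at least 104 Participants", giving as the reason: "This will allow room in case of patients are removed or fall from the study". No dropout rate is stated.

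No analysis population, missing-data method or missing-data sensitivity analysis appears. The nearest rules are in section 10, where an incompletely answered survey may be dropped, and section 9l, where a withdrawn participant's responses can be eliminated. Section 9g schedules surveys after the 6-week, 12-week and 6-month visits and none earlier.

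**The concern.** A two-sample t-test at 6 months uses only people with a 6-month score. Someone who answered at 6 and 12 weeks and then stopped contributes to those two tests and nothing to the third, although the earlier scores help to predict the missing one. The three tests may also describe three different sets of people.

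Two things are at stake. The first is precision, which is lost even if dropout is random. The second is bias, which arises if the link between score and loss differs by arm, or if the arms already differ when loss occurs. The protocol makes an arm-specific link plausible: sections 7 and 9g use a clinic tablet for in-person visits and an emailed link or a call for phone visits, and only phone participants may switch visit type.

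**Working it through.** **1. The plan's own figures.** Inputs from 9c and 9i: alpha 0.05, power 80%, standardised effect 0.8, and 1:1 allocation ("26 patients are required per group for a total of 52 Participants"). Sidedness is not stated; two-sided is inferred from the hypothesis of a difference.
- Exact two-sided t-test power (noncentral t): 79.1% at 25 per group and 80.7% at 26. So 26 reproduces.
- Implied allowance: 1 − 52/104 = 50%.

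**2. Assumptions not in the documents.** Scores have SD 1 and equal correlation ρ of 0.5 or 0.7 between visits; 52 are randomised per arm; everyone answers at 6 weeks; loss is permanent and totals 50% or 20% by 6 months. Where loss depends on score, the log-odds of loss change by 1 per SD of the previous score, with lower scorers more likely to leave.

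**3. Precision under random loss.** Let n1, n2, n3 be the numbers per arm answering at the three visits. The large-sample variance of an arm's 6-month mean is
- t-test: 1/n3
- likelihood model: (1 − R²)/n3 + (R² − ρ²)/n2 + ρ²/n1, with R² = 2ρ²/(1 + ρ).

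With n1, n2, n3 = 52, 39, 26 (25% lost by 12 weeks, then a third of the rest), the t-test variance is 1/26 = 0.0385.
- ρ = 0.5, R² = 0.333: 0.667/26 + 0.083/39 + 0.25/52 = 0.0326; ratio 0.85.
- ρ = 0.7, R² = 0.576: 0.424/26 + 0.086/39 + 0.49/52 = 0.0279; ratio 0.73.

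Simulation gives 0.86 and 0.73, so the model's variance is 14% to 27% smaller. Put the other way, the t-test's variance is 1/0.86 = 1.16 to 1/0.73 = 1.37 times the model's. At 20% loss the ratios are 0.94 and 0.89.

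**4. Bias, by simulation** (6,000 runs per scenario; ranges cover ρ 0.5 to 0.7; SD units; a positive bias favours the phone arm if higher scores are better).

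| Loss mechanism | True difference | Loss | t-test bias, 12 weeks | t-test bias, 6 months | Rejection at 6 months |
|---|---|---|---|---|---|
| Random | 0 | 50% | about 0 | about 0 | 5.0% |
| Same dependence in both arms | 0 | 50% | about 0 | at most 0.004 | 4.7% to 4.9% |
| Same dependence in both arms | 0.8 at all visits | 50%* | −0.05 to −0.07 | −0.09 to −0.12 | 79% to 81% (power) |
| Dependence in phone arm only | 0 | 50% | +0.12 to +0.17 | +0.23 to +0.32 | 13% to 21% |
| Dependence in phone arm only | 0 | 20% | +0.05 to +0.07 | +0.08 to +0.12 | 6.6% to 9.0% |

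*Set for no arm difference; the higher-scoring arm then loses fewer.

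A repeat simulation gave 12% to 21% in the fourth row. The likelihood estimate had 6-month bias within 0.01 SD in every row.

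**5. Do the rejection rates follow from the bias?** Rejection is about Φ(−1.96 + b/s) + Φ(−1.96 − b/s), with b the bias and s the simulated SD of the 6-month difference.
- 50% loss: 0.229/0.273 = 0.84 gives 13%; 0.315/0.266 = 1.18 gives 22%.
- 20% loss: 0.084/0.218 = 0.39 gives 7%; 0.124/0.217 = 0.57 gives 9%.

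These agree with the table.

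**6. Loss before the first survey.** Spread the same 50% equally over the three visits, with loss before 6 weeks depending on unrecorded earlier status. In the phone-only scenario the model is then biased by +0.09 to +0.13 SD, against +0.24 to +0.33 for the t-test. With 30% lost before 6 weeks the model's bias is +0.12 to +0.18. Under random loss spread this way, the variance gain falls to 9% to 20%.

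**The case against.** The strongest reply is that the t-test is not wrong in itself. With 26 per group at 6 months and random loss it has 80.7% power, which is the plan's target; the precision gain is then an improvement, not the repair of an error. No document figure supports any particular loss mechanism, slope or correlation. This stands, and the sizes above are illustrations under stated assumptions.

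A reader might also infer more than the documents support:
- *That any score-dependent loss biases the comparison.* It does not. With the same dependence in both arms and no true difference, bias is at most 0.004 SD and the error rate stays near 5%.
- *That the plan expects to lose half of those randomised.* Section 9c gives a recruitment target and no dropout rate. Sections 9a and 15 allow consent before the 2-week visit, while 9g places randomisation for follow-up after that visit, so some loss may precede randomisation.
- *That collected scores are thrown away.* Each usable score enters its own visit's test; it is only not used for later visits.
- *That a mixed model removes the problem.* It corrects for loss explained by observed scores. It cannot recover people lost before the 6-week survey, nor withdrawn participants whose responses are eliminated under 9l.

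What survives is that 9i has no method that links visits within a participant for the arm comparison, and nothing for missing scores, in a trial that recruits twice the number it needs.

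**Conclusion.** The concern holds in this limited form. As written, the 12-week and 6-month comparisons make no use of earlier scores from people lost later. The price in precision under random loss depends on how much loss there is and when: the model's 6-month variance is 14% to 27% smaller at 50% loss after 6 weeks, and 6% to 11% smaller at 20%.

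Bias is conditional. It is absent with a common mechanism and no true difference. It is about 0.1 SD of attenuation at 6 months with a common mechanism and the plan's own 0.8 effect. It is about +0.23 to +0.32 SD at 50% loss, with 12% to 21% false rejection, if only phone-arm loss depends on score. All of this rests on the assumed correlation of 0.5 to 0.7, the assumed slope, and full response at 6 weeks. The sample size of 26 per group is not in question. The change should be made because it is cheap and needs a weaker assumption about loss, not because bias has been shown.

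**What to change.** In section 9i, replace the per-visit t-tests with one linear mixed model for repeated measures for PROMIS Global, and likewise for KOOS, QuickDASH and satisfaction:
- fixed effects for arm, visit and arm-by-visit; unstructured within-participant covariance; REML with Kenward-Roger degrees of freedom;
- every randomised participant with at least one score, analysed in the arm assigned, whatever type of visit was attended;
- the arm difference with a 95% CI at each visit.

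Keep the t-tests as supportive. Add a sensitivity analysis, such as a delta-adjusted one, for loss that depends on unobserved scores.

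The de-identification text in 9i must change too. It removes all identifiers before analysis, so it should say that a coded study ID stays in the file and that visits remain linked within participant.

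The cost is a few sentences of plan wording, slightly more analysis work and a retained code, which may need matching wording on confidentiality. No extra patients, visits or surveys are needed.

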The Participant will be notified at the 2-week post-op or after if they will receive in-person follow up or virtual phone follow-up. If the Participant in the virtual phone group feel they need an in-person visit, the Participant will be free to make an in-person follow-up. After each follow up visit (6-week, 12-week, and 6-month), the Participant will be asked to fill out 30-minute surveys.

The surveys the Participant will be asked to fill out are the following:

1. KOOS- a knee specific survey
2. Quick Dash Outcome Measure
3. PROMIS Global
4. General Health Questionnaires (2)
5. Patient Satisfaction Survey -We will have the patient complete this also after every visit to see if their preferences change over time as their recovery changes.

If a Participant attends an in-person post-operative follow up visit, then the study team member will check to see if the participant is on the in-person list. If the participant is on the list, then he or she will be given a tablet to fill out the online survey after the appointment. The tablet will be set up so a link to the surveys can be accessed and participants can fill out the surveys. The surveys are on REDCaps (<https://research.lundquist.org/redcap/surveys/?s=NK3YH4NWL3>). Patients will be able to fill out the survey at home. For Participants that attend a virtual appointment, an online

Patient reported outcomes from patients seen in virtual phone visits compared to in-person physical visits for post-operative follow-up at a sports medicine clinic: a prospective randomized controlled trial

link to the survey on REDCap will be sent to the Participant's email. Members of the study team can also call the participant to conduct the survey over the phone. The emails will be made secure by having them sent out from an official DHS email that uses Microsoft outlook and requires double verification to logon. The content of the email message is included in the IRB submission as a separate document.

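### The Analysis of Variance for change in satisfaction over three visits names no participant term; run as a one-way analysis, it would be conservative for any positive within-person correlation

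*Combined protocol and SAP*

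**What the plan says.** Section 9g sets out the repeated measurement: "After each follow up visit (6-week, 12-week, and 6-month), the Participant will be asked to fill out 30-minute surveys". On the satisfaction survey it adds: "We will have the patient complete this also after every visit to see if their preferences change over time as their recovery changes". One person therefore contributes up to three satisfaction scores.

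Section 9i gives the test. Within each category, to find out whether participants' "satisfaction changed as time progressed, we will conduct an Analysis of Variance". The stated purpose is to learn whether satisfaction with phone visits shifts as time since surgery grows. The section does not say whether the analysis is one-way or repeated-measures. It names no participant effect, sphericity correction or rule for missing visits. The other tests it names, a Student t-test and a chi-squared test, both compare the two groups.

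On the analysis file, section 9i says that at export "all identifiers will be removed and a de-identified data set is maintained and analyzed". It does not say whether a code joining one person's three surveys is kept.

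**The concern.** Change over time in the same people is a within-person question. A one-way ANOVA with visit as the factor treats three scores from one person as scores from three different people. Some people rate generously and others harshly at every visit. Those stable differences cancel out of the comparison between visits, but they remain in the one-way error term. The F ratio is then too small on average and the p-value too large.

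At stake is the plan's only analysis of whether satisfaction with phone follow-up changes over time. The weaker test would miss real changes more often than the same data require. A within-person analysis also needs the three records of each person to be linked in the file that is analysed, and the plan does not secure this in writing.

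**Working it through.** **The plan's own figure.** Section 9i states "Power of 80%, and assuming a large effect size of 0.8, 26 Participants are required per group for a total of 52 Participants". For a two-sided two-group t-test at 0.05, the normal approximation gives n = 2(1.96 + 0.84)²/0.8² ≈ 24.5, so 25. The t-based solution is 25.52, so 26, with power 80.7%. The figure reproduces. It belongs to the between-group comparison; the plan gives no calculation for the satisfaction ANOVA.

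**Inputs from the documents.** Three visits (section 9g). A significance level of 0.05: "Statistical significance will be based on an α level of 0.05" (section 9i). 26 per group (sections 9c and 9i). Up to 52 per group if everyone recruited contributes, since section 9c says "Locally we will attempt to recruit at least 104 Participants" and 104/2 = 52.

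**Assumptions, not in the documents.** Normal scores with SD 1 at each visit, the same correlation ρ between any two visits (compound symmetry), ρ from 0 to 0.7, complete data, and for power a linear drift totalling 0.5 SD (visit means 0, 0.25, 0.5).

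**Why the direction is fixed.** With n people and no true change:

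- The visit mean square has expectation 1 − ρ.
- The one-way error mean square is [(1 − ρ)A + (1 + 2ρ)B]/[3(n − 1)], with A chi-squared on 2(n − 1) df and B chi-squared on n − 1 df. Its expectation is [2(1 − ρ) + (1 + 2ρ)]/3 = 1, whatever ρ is.
- The repeated-measures error mean square has expectation 1 − ρ, matching the numerator.

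So the one-way F is too small by a factor of roughly 1 − ρ for any ρ above zero.

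**Type I error.** In large samples it is P(χ²₂ > 5.99/(1 − ρ)) = 0.05^(1/(1 − ρ)): 3.6% at ρ = 0.1, 1.4% at 0.3, 0.25% at 0.5. The table uses the finite-sample version, with one-way critical value F(2, 75) = 3.12 and the error mean square above.

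**Power.** The noncentrality is λ = n Σ(μⱼ − μ̄)²/(1 − ρ) = 26 × (0.0625 + 0 + 0.0625)/(1 − ρ) = 3.25/(1 − ρ). The one-way test rejects when a noncentral χ²₂(λ) exceeds 2 × 3.12 × (error mean square)/(1 − ρ). The repeated-measures test uses the noncentral F(2, 50) with critical value 3.18.

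| ρ (assumed) | One-way type I error, n = 26 | Power, one-way | Power, repeated-measures |
|---|---|---|---|
| 0 | 5.0% | 33% | 33% |
| 0.1 | 3.6% | 32% | 36% |
| 0.3 | 1.5% | 28% | 45% |
| 0.5 | 0.4% | 23% | 59% |
| 0.7 | below 0.1% | 16% | 82% |

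A simulation of 200,000 trials per setting agrees to within 0.1 percentage point on type I error and, for positive ρ, 0.2 points on power. The repeated-measures test held 4.9% to 5.1% under no change.

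**Sensitivity.**

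- With 52 per group and ρ = 0.5, power is 60% one-way against 90% repeated-measures.
- If correlation decays with distance between visits (AR(1)), one-way type I error with 26 per group is 2.3%, 0.9% and 0.2% at 0.3, 0.5 and 0.7. The direction is the same and the effect milder. Repeated-measures ANOVA without a sphericity correction then reaches up to 5.6%, which is why the correction belongs in the fix.

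**The case against.** **The plan does not prescribe a one-way test.** A reader might infer that it does. Repeated-measures ANOVA is also an Analysis of Variance, and the wording about change over time fits it. This stands: what is certain is that the type is left open. It remains worth fixing, because the two readings give very different answers at moderate correlation and every other test named in section 9i is for independent groups.

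**The size is not known.** A reader might conclude that the test is severely conservative as a matter of fact. The documents give no correlation, satisfaction scale or SD. At ρ = 0.1 the loss is slight (3.6% against 5%; 32% against 36% power). It becomes severe only around 0.5 and above.

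**A null result would not be empty.** A reader might infer that a one-way analysis could never show a real change. That is false. Take a total drift of 0.8 SD, borrowing the effect size that the plan states for its between-group comparison. Then λ = 26 × (0.16 + 0 + 0.16)/(1 − ρ) = 8.32/(1 − ρ), and one-way power with 26 per group is 72% to 77% for ρ from 0.1 to 0.7. Conversely, for a 0.5 SD drift at ρ of 0.3 to 0.5, the repeated-measures test reaches only 45% to 59%, so a null result would not establish stability after the fix either. Nor does the plan say that it would read a null that way.

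**Linkage is not shown to be lost.** Removing identifiers concerns identity. Participants are numbered at enrolment (section 9g), the separate participant list carries a study ID (section 9j), and a file with one row per person would keep visits together. This too stands: the documents support a risk, not a finding that linkage is broken.

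**Conclusion.** The point holds in conditional form. The same people answer three times and section 9i names no participant term. If the analysis is run as a one-way ANOVA by visit, it is conservative for any positive within-person correlation. Under the stated model with 26 per group, the power lost on a 0.5 SD drift runs from about 4 percentage points at ρ = 0.1 (36 − 32) to about 66 at ρ = 0.7 (82 − 16). These sizes rest on an assumed correlation, normal scores, compound symmetry, complete data and a linear drift.

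The reach is limited. Satisfaction is a secondary endpoint (section 9f) and this is a within-group question. A reader should not carry the point over to the primary PROMIS Global t-test, the between-group satisfaction comparison or the sample size, none of which it touches. The change is still worth making: it costs almost nothing, and at zero correlation the two methods have essentially the same power.

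**What to change.** In section 9i, replace the unqualified reference to Analysis of Variance with a named method: within each group, a linear mixed model for satisfaction with visit as a fixed effect and participant as a random effect. Repeated-measures ANOVA with a sphericity correction would also serve. The mixed model has the advantage of using people with only one or two completed visits. That matters because section 10 lets participants stop at any time and allows incomplete surveys to be removed.

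In the export text of the same section, state that a non-identifying participant code is kept in the de-identified file so that each person's three surveys stay linked. Settle this before the export, since section 9i says that the team cannot match data to participants afterwards.

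The cost is one sentence on the method, one on the code, and one column in the file. No new patients, visits or data are needed. The downside is slightly more analysis work than a one-way ANOVA in a spreadsheet.
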